**Subcutaneous Administration of Casirivimab+Imdevimab in Clinical Trials.**

*Prophylaxis Setting.* In COV-2069 (R10933-10987-COV-2069), the phase 3 prevention trial in those at high risk of infection by a household contact, a single subcutaneous dose of casirivimab+imdevimab (1200 mg) reduced (relative to placebo) symptomatic SARS-CoV-2 infection by 81.4%, and reduced overall SARS-CoV-2 infection by 66.4%. The incidence of serious adverse events was similar between the active treatment group (1%) and placebo group (1%). Injection-site reactions were more common in the treatment group (4%) compared to the placebo group (2%), and were all mild to moderate with injection-site reactions in the study grade 3 or above. The majority of injection site reactions occurred within one day and resolved within two days ([O'Brien, 2021c](#)).

Among a sub-group of individuals in COV-2069 who were identified as SARS-CoV-2 positive but asymptomatic during screening, a single subcutaneous dose of casirivimab+imdevimab (1200 mg) reduced (relative to placebo) progression to symptomatic disease by 31.5%, and reduced the duration of symptoms in those that developed symptomatic infections. Injection-site reactions were more common in the treatment group (4%) compared to the placebo group (1%), but no injection-site reactions in the study were grade 3 or above ([O'Brien, 2021b](#)).

In COV-2069, efficacy results were similar in adolescents (age 12 to <18) as observed in adults: 0% of subjects in the 1200 mg SC treatment group experienced symptomatic infection, compared with 9.3% of subjects in the placebo group. Safety data in adolescent subjects were also similar to that observed in adults. Injection site reactions were more common in the treatment group (5.9%) compared to the placebo group (1.6%), but none were grade 3 or above in any group.

*Adult Volunteers.* In HV-2093 (R10933-10987-HV-2093), an adult volunteer study evaluating repeated doses of subcutaneously-administered casirivimab+imdevimab 1200 mg SC (monthly dosing over 6 months), casirivimab+imdevimab was well-tolerated with no unexpected safety findings. The incidence of treatment-emergent AEs was higher in the active treatment group (52.7%) compared to placebo (46.3%). This difference was primarily due to a higher incidence of injection-site reactions in the casirivimab+imdevimab group (34.6%, compared with 15.8% in the placebo group), but none were grade 3 or above in any group. All injection-site reactions were thus mild or moderate in severity and most events resolved without treatment. Although very few participants experienced symptomatic SARS-CoV-2 infection in the study, infection was less common within the active treatment group (0.4%; 3 participants) compared with placebo (5.0%; 12 participants)

### 3.3.2. Summary of Risks

**Identified Risks.** As with other protein therapeutics, hypersensitivity reactions, including acute infusion-related reactions (intravenous administration) or injection site reactions (subcutaneous administration), may develop immediately or within a few hours to days after study drug administration. Hypersensitivity reactions, including infusion-related reactions or injection site reactions, have been observed in study participants who received casirivimab+imdevimab during ongoing clinical trials.

**Potential Risks.** The potential risks of casirivimab+imdevimab are the clinical consequences of immunogenicity and embryo-fetal toxicity.

Protein therapeutics carry the potential risk of an immunogenic response in the form of anti-drug antibody (ADA) and neutralizing antibody (NAb) development following administration, with possible consequences on safety and efficacy. Therefore, blood samples for immunogenicity assessment will be collected during the studies.

Reproductive and developmental toxicology studies have not been conducted, and the effects of casirivimab, imdevimab, or casirivimab+imdevimab combination therapy on the fetus and reproductive organs in males and females are unknown. There is also currently limited clinical experience in the use of casirivimab, imdevimab, or casirivimab+imdevimab combination therapy in females who are pregnant or breastfeeding.

Human IgG1 antibodies are known to cross the placental barrier and are present in breast milk. Casirivimab and imdevimab combination therapy therefore has the potential to be transferred from the mother to the developing fetus or a breastfed child. Given the high affinity and specificity of casirivimab+imdevimab, off-target pharmacological effects are not anticipated in either the mother or the fetus, and no off-target binding of casirivimab or imdevimab was observed in any of the human or monkey tissues evaluated *ex vivo* in tissue cross-reactivity studies. However, it is unknown whether the potential transfer of casirivimab+imdevimab combination therapy provides any treatment benefit or risk to the developing fetus or a breastfed child.

The combination of casirivimab+imdevimab therapy should be used during pregnancy or breastfeeding only if the potential benefit justifies the potential risk for the mother and the fetus or breastfed child considering all associated health factors. Pregnancy that occurs during this study will be reported and followed, including any complications and pregnancy outcome, as described in Section 10.1.3.

**Other Theoretical Risks.** Theoretical risks of casirivimab+imdevimab include interference with the participant's endogenous immune response to either SARS-CoV-2 infection or vaccination against COVID-19. This study will enroll individuals with a demonstrated non-response to COVID-19 vaccination (Section 7.2), regardless of prior passive antibody therapy. This theoretical risk is therefore unlikely to apply to the study population.

Antibody-dependent enhancement (ADE) has been observed for some therapeutics targeting exogenous viral proteins. Clinical trials of casirivimab+imdevimab, including analyses of post-treatment follow-up periods in studies COV-2069 and COV-2093, have not identified any evidence of an increase in reinfection corresponding to the waning effect of antibody treatment. To assess any potential ADE, a similar approach as that of COV-2069 and COV-2093 will be adopted in this study: All participants will have follow-up assessments during the drug elimination period (for over five half-lives), and participants will be monitored for any signal of ADE.

### 3.3.3. Summary

The available clinical and nonclinical data for casirivimab+imdevimab demonstrates anti-viral efficacy with a favorable safety profile. Based on these data, and given the current unmet need for prophylactic therapies to prevent SARS-CoV-2 infection and COVID-19 disease in immunocompromised individuals, it is the opinion of the Sponsor that the overall risk-benefit balance for casirivimab+imdevimab is acceptable to allow evaluation of casirivimab+imdevimab in the study population.

## 4. ENDPOINTS

### 4.1. Primary Endpoint

The primary endpoint is cumulative incidence of symptomatic (broad term), RT-PCR-confirmed SARS-CoV-2 infection cases during the efficacy assessment period (EAP).

*Note: definitions of symptomatic SARS-CoV-2 infection and the EAP are provided in Section 6.2.*

### 4.2. Secondary Endpoints

The secondary endpoints are:

- Proportion of participants with grade  $\geq 3$  treatment-emergent adverse events (TEAEs), during the EAP and follow-up period
- Proportion of participants with TEAEs leading to study drug discontinuation, during the EAP and follow-up period
- Proportion of participants with treatment-emergent serious adverse events (SAEs) during the EAP and follow-up period
- Incidence of adverse events of special interest (AESIs) during the EAP
- Concentration of each mAb (as applicable to the treatment arm) over time
- Incidence and titer of anti-drug antibodies (ADA), and incidence of neutralizing antibodies (NAb) to each mAb (as applicable to the treatment arm) over time

### 4.3. Exploratory Endpoints

The exploratory endpoints are:

- Cumulative incidence of symptomatic (broad term), RT-PCR-confirmed SARS-CoV-2 infection cases during the follow-up period
- Cumulative incidence of RT-PCR-confirmed SARS-CoV-2 infection cases (regardless of symptoms) during the EAP
- Proportion of participants with  $\geq 1$  moderate COVID-19 symptom (broad term) during the EAP and follow-up period
- Duration of COVID-19 signs and symptoms in weeks (broad term) after diagnosis
- Proportion of participants with COVID-19-related hospitalization, emergency room visit, urgent care center visit or death during the EAP and follow-up period
- Proportion of participants with COVID-19-related hospitalization or death during the EAP and follow-up period
- Proportion of participants requiring supplemental oxygen due to COVID-19 during the EAP and follow-up period
- Proportion of participants admitted to an intensive care unit (ICU) due to COVID-19 during the EAP and follow-up period

- Proportion of participants requiring mechanical ventilation due to COVID-19 during the EAP and follow-up period
- Proportion of symptomatic (broad term) participants with viral load  $>4 \log_{10}$  copies/mL in NP swab sample collected at the time of COVID-19 diagnosis
- Maximum SARS-CoV-2 RT-qPCR viral load ( $\log_{10}$  copies/mL) in NP swab samples among individuals with  $\geq 1$  RT-qPCR positive test that has an onset during the EAP
- Number of weeks of viral load  $>4 \log_{10}$  copies/mL in NP swab samples among symptomatic (broad term) participants during the EAP
- Viral variant characteristics of SARS-CoV-2 in participants who become infected post-baseline

## 5. STUDY VARIABLES

A summary of study variables is provided below. A full accounting of variables will be provided in the statistical analysis plan (SAP).

### 5.1. Demographic and Baseline Characteristics

The variables for baseline characteristics include standard demography (eg, age, race, weight, height), medical history, vaccination history, and medication history.

### 5.2. Efficacy Variables

Efficacy variables include number of participants with symptomatic RT-qPCR-confirmed SARS-CoV-2 infection and viral load ( $\log_{10}$  copies/mL).

### 5.3. Safety Variables

Safety variables include recordings or measurements for individual participants of targeted TEAEs, vital signs, and laboratory test results.

### 5.4. Pharmacokinetic Variables

The PK variables are concentrations of casirivimab and imdevimab in serum and time. The sampling time points are specified in [Table 1](#).

### 5.5. Immunogenicity Variables

The immunogenicity variables are ADA status, titer, and NAb status at nominal sampling time/visit. Serum samples for ADA will be collected at the visits specified in [Table 1](#). Samples positive in the ADA assays will be further characterized for ADA titers and for the presence of NAb.

## 6. STUDY DESIGN

[figure not shown]
### 6.1. Study Description and Duration

This is a randomized, double-blind, placebo-controlled, phase 3 study to assess the safety and efficacy of casirivimab+imdevimab as pre-exposure prophylaxis against symptomatic COVID-19 in immunocompromised individuals, defined according to the primary and secondary immunodeficiencies outlined in the study eligibility criteria (Section 7.2).

The study consists of three periods: a screening period of up to 14 days, an efficacy assessment period (EAP) of approximately 6 months (precise definition provided in Section 11.4.3.1), and a 3-month follow-up period. A diagram depicting the study design is provided in Figure 1. The Schedule of Events is provided in Section 9.1.

In addition to the main study, an optional immunology sub-study will be conducted outside of the protocol.

**Figure 1: Study Flow Diagram**

### 6.2. Evaluation of Symptomatic SARS-CoV-2 Infection

The primary endpoint of the study will evaluate **symptomatic SARS-CoV-2 infection cases**. The conditions for symptomatic SARS-CoV-2 infection are as follows:

- At least 1 sign or symptom (broad term definition) confirmed by a study clinician (investigator or designee) to be related to COVID-19, **and**
- A positive SARS-CoV-2 RT-PCR result (local or central analysis), **with**

- The sign/symptom onset date and the date of collection for the positive sample occurring within  $\pm 7$  days of one another

The primary endpoint will analyze symptomatic SARS-CoV-2 infection during the efficacy assessment period (EAP), whose definition is provided in Section [11.4.3.1](#).

**Broad Term** COVID-19 signs and symptoms include fever  $\geq 38.0^{\circ}\text{C}$  as well as 23 sign/symptoms designed to be consistent with the Symptom Evolution of COVID-19 (SE-C19) instrument developed by the Sponsor. Broad term signs and symptoms are listed in [Table 3](#).

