### Optional Dose

The Sponsor believes that casirivimab+imdevimab may continue to serve as an important pre-exposure prophylaxis therapeutic among immunocompromised individuals in regions where Omicron is not the dominant variant or in regions where Omicron prevalence subsides. For this reason, participants will have the option to receive a 1200 mg SC dose of casirivimab+imdevimab as a final study dose. This optional dose may be administered to all participants regardless of treatment assignment at randomization. However, participants will not be eligible to receive this dose if they have already received casirivimab+imdevimab as post-infection treatment.

Participants will be asked to return to the site for an unscheduled visit, during which they will be asked to consent to protocol amendment 2 and receive the final optional dose, if desired. This visit to receive the final optional dose should occur approximately 4 weeks after the most recent dose. Note that consent may be obtained remotely prior to this visit, if available and allowable by the study site.

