4.5. Efficacy Variable

4.5.1. Primary Efficacy Variable

Primary efficacy variable is cumulative incidence of symptomatic (broad term), RT-PCR-confirmed SARS-CoV-2 infection cases during the efficacy assessment period (EAP). The conditions for symptomatic SARS-CoV-2 infection are as follows:

- At least 1 sign or symptom (broad term definition) confirmed by a study clinician (investigator or designee) to be related to COVID-19, **and**
- A positive SARS-CoV-2 RT-PCR result (local or central analysis), **with**
- The sign/symptom onset date and the date of collection for the positive sample occurring within ± 7 days of one another

The primary endpoint will analyze symptomatic SARS-CoV-2 infection during the efficacy assessment period (EAP). The EAP is defined as the day 2 to day 169 +7 days . In addition, following rules will be applied to the primary analyses:

- Time to first symptomatic infection is defined as the first date of having either central or local lab determined positive test result.
- Subjects do not experience any symptomatic infection will be censored at last observed time point.
- Subjects who die at any time in the study or discontinue the study earlier (did not get any infections) will be censored at the end of study in case of final database lock.
- Subjects with COVID-19 symptoms that are missing a central lab determined RT-qPCR test during the EAP but have a positive SARS-CoV-2 test from a local lab will be considered as having a symptomatic infection if any of the symptoms occurred within 7 days of the positive SARS-CoV-2 test that was observed during the EAP.
- If subjects took optional dose of 1200mg, all the data after the dose will be removed from the efficacy analyses.

If subjects took investigational, authorized, or approved COVID-19 vaccines within 90 days of the last dose of study drug (or per current CDC recommendations) (CDC, 2021) or any covid-19 treatment medications for prevention after starting study treatment (Anti SARS-CoV-2 antibodies including Bamlanivimab/ Etesevimab, Casirivimab/ Imdevimab (REGEN-COV), Sotrovimab or Tixagevimab/ Cilgavimab (Evusheld); remdesivir; Nirmatrelvir/ Ritonavir (Paxlovid); Molnupiravir, all the efficacy data after these treatment will be removed from efficacy analyses.

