5.7.1. Analysis of Primary Efficacy Endpoint

The mITT population will be the primary analysis population for efficacy. The ITT population will also be used for primary efficacy analysis. Participant data will be analyzed according to the group to which they were randomized.

The primary endpoint of the study is cumulative incidence of symptomatic (broad term), RT-PCR-confirmed SARS-CoV-2 infection cases during the efficacy assessment period (EAP). See Section 4.5.1 for the definition of a symptomatic SARS-CoV-2 infection.

The cumulative incidence of cases through the EAP will be estimated using the Kaplan-Meier method, and the antibody efficacy (AbE) will be estimated as the percent risk reduction (ie, $100 \times [1-HR]$, where HR is the hazard ratio for comparison of the incidence of cases in the antibody arm versus placebo). A unstratified Cox proportional hazard regression model with treatment group as a fixed effect, will be used to estimate the hazard ratio and 95% CI (2-sided). Nominal two-sided p-values will be reported for descriptive purpose using the log-rank test for pairwise comparison between each antibody arm and placebo.

For the primary analysis, cases will be counted from day 2 through day 176 (ie, day 169 +7 days), to allow for cases to accrue until the end of the EAP visit window per the Schedule of Events. Time of symptomatic SARS-CoV-2 infection will be the earlier of the sign/symptom onset date or the sample collection date for which RT-PCR result (local or central) was positive.

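### The optional-dose cut in SAP 4.5.1 is worded by data rather than by event date, so read literally it drops a primary case that began before the dose and was confirmed after it (minor)

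*Protocol*

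**What the plan says.** **Case definition.** Protocol 6.2 and SAP 4.5.1 require a clinician-confirmed broad-term sign or symptom and a positive RT-PCR, with "The sign/symptom onset date and the date of collection for the positive sample occurring within" 7 days of one another, in either direction.

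**Cut at the optional dose.** SAP 4.5.1: "If subjects took optional dose of 1200mg, all the data after the dose will be removed from the efficacy analyses". The next paragraph there applies a similar cut after COVID-19 vaccines or preventive anti-SARS-CoV-2 products.

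**Event date.** SAP 5.7.1: "Time of symptomatic SARS-CoV-2 infection will be the earlier of the sign/symptom onset date or the sample collection date for which" the RT-PCR was positive. SAP 1.1 and Protocol 11.4.3.1 give the same rule. SAP 4.5.1 differs: "Time to first symptomatic infection is defined as the first date of having either central or local lab determined positive test result".

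**No counted case.** SAP 4.5.1: "Subjects do not experience any symptomatic infection will be censored at last observed time point".

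**Access to the optional dose.** Protocol Amendment 2 Procedures, Optional Dose: "This optional dose may be administered to all participants regardless of treatment assignment at randomization". The one stated bar is that "participants will not be eligible to receive this dose if they have already received casirivimab+imdevimab as post-infection treatment".

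**The concern.** The endpoint has two dated parts that may lie up to 7 days apart, while the cut acts on data on one side of a single date. If the dose falls between the two parts, the cut can remove the second part and leave the first unable to qualify. An infection whose onset came under randomised treatment would then be analysed as no infection. The same section also dates the event differently from SAP 5.7.1, so two programmers could handle the same participant differently and both claim to follow the SAP.

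What is at stake is the count of primary cases, and with it the Kaplan-Meier incidence, the hazard ratio with its 95% CI and the nominal p-values that SAP 5.7.1 still plans to report. Safety analyses are not affected.

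**Working it through.** **1. The rules applied to one participant.** For illustration, take a participant whose last assigned dose was on day 29 and whose optional dose is on day 57 (28 days later, as in Protocol Table 2).

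| Reading of the cut | Event date used | Onset day 55, positive sample day 58 | Positive sample day 55, onset day 58 |
|---|---|---|---|
| By record | either | sample removed, case lost | symptom removed, case lost |
| By case | SAP 5.7.1 (earlier part) | dated day 55, counted | dated day 55, counted |
| By case | SAP 4.5.1 (first positive test) | dated day 58, not counted | dated day 55, counted |

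The SAP does not say whether the cut is by record or by case. The wording, which refers to all the data, fits the by-record reading better.

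**2. Can this arise under Amendment 2?**
- The Table 2 dose visit schedules no dedicated COVID-19 symptom assessment and no swab.
- The suspected-COVID visit is optional. Symptoms may be assessed remotely, with a site swab later.
- Current symptoms and pending tests are not named as bars to the dose.

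The symptom-first order is therefore open. The sample-first order is much narrower. Study samples are taken once a clinician has linked a symptom to COVID-19 (Protocol 6.4.2 and Amendment 2), so onset normally precedes the sample. What remains is mainly a positive RT-PCR obtained outside the study, which Protocol 6.4.3 accepts.

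**3. Check of the planning incidence.** Inputs from Protocol 11.1, 11.2 and Table 6: placebo incidence 4.02% over 6 months; hazard ratios 0.40, 0.45 and 0.55; 5% dropout by 6 months; 2188 per arm, 90% in the mITT set.
- Placebo hazard h = -ln(1 - 0.0402) = 0.0410 per 6 months; dropout hazard g = -ln(0.95) = 0.0513.
- Expected cases per arm = 0.9 x 2188 x [h·HR/(h·HR + g)] x [1 - exp(-(h·HR + g))].
- Result: 77.2, 31.2, 35.1 and 42.8, total 186.4. Table 6 gives 77, 31, 35, 43 and 186, so the planning figures reproduce.

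**4. Expected straddling cases.** Daily placebo hazard = 0.0410/182.6 = 0.000225. The mean hazard ratio over four equal arms is (1 + 0.40 + 0.45 + 0.55)/4 = 0.60, so the arm-average daily hazard is 0.000135. Expected straddling cases = 66 x daily hazard x gap in days. Uptake of the dose is not given; using all 66 gives an upper bound. The gap is also assumed: 2 days matches the 48-hour evaluation target, and 7 days is the longest gap the definition allows.

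| Assumed incidence | 2-day gap | 7-day gap |
|---|---|---|
| Planned, arm average | 0.018 | 0.062 |
| Planned placebo rate in all arms | 0.030 | 0.104 |
| Ten times planned, arm average | 0.18 | 0.62 |

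At planned arm-average rates the chance of at least one such case is 1.8% to 6.0%; at ten times those rates it is 16% to 46%.

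**5. Weight of one case.** 66/4 = 16.5 per arm, so one case is 1/17 to 1/16 = 5.9% to 6.3% of an arm.

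**The case against.** The strongest case against acting is that this hardly matters. SAP section 1 says that none of the hypotheses can be evaluated and that all endpoints are now exploratory. Amendment 2 makes every analysis descriptive, and the expected number of affected cases is far below one. That stands, and it sets the severity.

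A second objection is that a sensible programmer would cut by case and use the SAP 5.7.1 date, which keeps the case. That reading is possible but not written down, and SAP 4.5.1 itself supplies an event date that gives the opposite answer for the symptom-first case.

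A third is that symptoms could surface at the dose visit, since adverse events and pre-dose vital signs, including temperature, are collected there. True, but no rule links those findings to case status or to the cut.

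A reader might also infer more than the documents support:
- *That up to a quarter of pre-dose cases are lost.* The share lost is mean gap divided by days at risk. At 28 days it is 2/28 = 7.1%; 7/28 = 25% needs every case to have the longest allowed gap.
- *That these shares apply to about 1.6 cases.* That figure, 16.5 x (0.0402 + 0.01628 + 0.01829 + 0.02231) = 1.60, covers a full 6 months. Before the dose the expected total is 66 x 28 x 0.000135 = 0.25 for 28 days at risk, and 0.75 for 84 days.
- *That both orders are equally exposed.* A pending central result loses nothing, because the collection date is what counts.
- *That the data are discarded altogether.* The removal covers the efficacy analyses only.

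**Conclusion.** The concern holds as a minor defect in SAP 4.5.1. The case definition in Protocol 6.2 is not at fault. Applied literally, the optional-dose cut discards a case that SAP 5.7.1 dates before the dose, and the two event dates in the SAP leave the case's status unresolved even if the cut is applied by case.

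The expected loss is about 0.02 to 0.06 cases at planned rates. This assumes a constant hazard, all 66 participants taking the dose and a gap of 2 to 7 days. It would matter only if such a case occurred. It would then shift one arm by about 6 percentage points and could remove that arm's only event. The documents do not support a claim of material bias in the treatment comparison.

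**What to change.** 1. Use one event date throughout: the earlier of symptom onset and positive sample collection, as in SAP 5.7.1. Delete or align the first-positive-test bullet in SAP 4.5.1. Changing the dose bullet alone would leave that conflict in place.
2. Replace the optional-dose bullet with: *For efficacy, participants who take the optional dose are censored at the dose date. A case whose event date is on or before the dose is counted even if its second component falls after the dose but within 7 days of the first. Cases with an event date after the dose are not counted.*
3. Use the same event-date wording for the cut after COVID-19 vaccines or preventive anti-SARS-CoV-2 products in SAP 4.5.1.

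The cost is a few sentences in the SAP and a small programming change, with no new data. The downside is that a few samples collected after the dose are used. Broad-term symptoms such as headache, fatigue or sneezing are non-specific, so a later positive sample may not always reflect an infection that began before the dose. List any straddling case individually so that a reader can judge it.
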